Study protocol

Effects of High Intensity Focused Electromagnetic Therapy with Pelvic Floor Muscle Training on Urine Leakage and Quality of Life in Primipara or Multipara Women with Stress Urinary Incontinence: A Pilot for Randomised Controlled Trial

Objectives

This study aimed to evaluate the impact of High-Intensity-Focused-Electromagnetic-Therapy (HIFEM) combined with Pelvic-Floor-Muscle-Training (PFMT) versus PFMT alone on urine leakage and quality of life in Primipara or Multipara women with stress urinary incontinence.

Method

Ethical committee approval

This study protocol was approved by the Ethics Committee of Hong Kong Metropolitan University (reference number: N&HS00004).

Sample size calculation

The sample size was determined based on the observations of the primary outcome (the 1hour pad test) in a previous study. Using version 3.1.9.4 of the G*Power statistical software, a minimum sample size of 42 (21 per arm) was established. The a priori power analysis utilized an estimated effect size of 0.9, with a 95% confidence interval ($\alpha \le 0.05$), statistical power of 80%, and a 1:1 allocation ratio. Anticipating a 20% dropout rate, the calculated size was adjusted to 50 subjects (25 per group).

Participants

Ambulatory and community-dwelling primipara or multipara women aged ≥ 30 years with Stress Urinary Incontinence (SUI) symptoms confirmed by the International Consultation on Incontinence Questionnaire-Urinary Incontinence Short Form (ICIQ-UI-SF) were recruited if they agreed not to seek any other form of treatment for SUI during the study. Those with contraindications for High-Intensity Focused Electromagnetic Therapy (HIFEM) were excluded. Other exclusion criteria included prior surgery for incontinence, use of medications for bladder dysfunction or diuretics, hormone therapy, urgent or mixed urinary incontinence, incontinence associated with a neurological condition, inability to perform voluntary pelvic floor muscle contractions, cognitive impairment or dementia, major neurological disorders (such as stroke, cerebral palsy, and multiple sclerosis), inability to carry out the treatment or evaluation, and uncontrolled hypertension.

Procedure

Interventions: Subjects were randomized into two treatment groups. The experimental group received both HIFEM and Pelvic Floor Muscle Training (PFMT), while the control group received only PFMT. The treatment continued for 6 weeks.

HIFEM: HIFEM stimulation was administered using an Emsella instrument (manufactured by BTL Industry Inc., Boston, MA) according to the manufacturer's protocol. The frequency ranged between 50 and 60 Hz, and the intensity was set as high as the patient could tolerate, typically up to 100%.

The PFMT protocol followed guidelines outlined in a previous study. Participants were instructed to perform 5 rapid contractions over a span of 3 seconds, followed by 10 prolonged contractions, each lasting between 3 to 8 seconds, with 10-second intervals for relaxation in

between, all while in a crook-lying position.

Measurements

Evaluations conducted at baseline and after the six-week intervention. Measurements included the 1-hour Pad Test, the International Consultation on Incontinence Questionnaire-Urinary Incontinence Short Form (ICIQ-UI-SF), and sonography to assess bladder neck movement.

1-hour pad test: The total amount of urine leakage was measured by weighing the pad after performing several standardized activities over the course of an hour.

ICIQ-UI-SF: The ICIQ-UI-SF was used to assess the frequency and severity of SUI and its impact on quality of life. The scores from these items provide an overall score ranging from 0 to 20, with higher scores indicating greater severity of urinary incontinence and a more significant impact on quality of life.

Bladder neck movement: Bladder neck movement was measured using an ultrasound scanner. The ultrasound scanner is a Clarius C3 HD3 (Clarius Mobile Health, Vancouver, Canada).

Statistical analysis

All data were analyzed using IBM SPSS Statistics for Windows, Version 26.0 (Armonk, NY: IBM Corp). A two-way repeated measures ANOVA was employed with the outcome metrics, both pre- and post-intervention.

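### The dropout allowance is miscalculated: 50 women enrolled with 20% dropout leaves 40 evaluable, below the plan's own minimum of 42

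*Combined protocol and SAP*

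**What the plan says.** The Sample size calculation section bases the size on the 1-hour pad test, the primary outcome, as observed in a previous study. On effect size it says: "The a priori power analysis utilized an estimated effect size of 0.9". Alpha is 0.05, power is 80%, and the design has "a 1:1 allocation ratio". From these inputs, using G*Power, "a minimum sample size of 42 (21 per arm) was established". The next step is the dropout adjustment: "Anticipating a 20% dropout rate, the calculated size was adjusted to 50 subjects (25 per group".

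The section gives no formula for the adjustment. It does not name the test behind the G*Power calculation or say whether alpha is one- or two-sided.

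The Measurements section has assessments only at baseline and after six weeks. The Statistical analysis section plans a two-way repeated measures ANOVA on the pre and post values and gives no method for missing post-intervention data.

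**The concern.** A dropout adjustment exists so that the required number of evaluable participants remains after the expected loss. Here the plan's own three figures (a minimum of 42, a 20% loss and 50 enrolled) do not fit together. The likely cause is that the minimum was increased by 20%, when it should have been divided by the proportion expected to stay.

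At stake is the claim that the enrolled size protects 80% power on the primary outcome. A woman without a six-week value has no post score to enter the planned pre-post analysis, and no method for handling her is given. Completers are therefore the relevant count.

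**Working it through.** **Inputs, all from the Sample size calculation section:** minimum 42 (21 per arm); effect size 0.9; alpha 0.05; power 80%; 1:1 allocation; dropout 20%; enrolled 50 (25 per group).

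**Assumptions, because the plan does not say:** 0.9 is a standardised mean difference *d*, and the test is a two-sided two-sample t-test with power from the noncentral t distribution.

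**1. Reproduce the plan's minimum.** With *n* per arm, the noncentrality parameter is *d*·√(*n*/2) on 2*n* − 2 degrees of freedom. Solving for 80% power at *d* = 0.9 and two-sided alpha 0.05 gives *n* = 20.39, so 21 per arm and 42 in total. This matches the plan exactly. A one-sided t-test gives 16 per arm (32 in total), and the two-sided normal approximation gives 20 per arm (40 in total). Neither returns 42, so the two-sided t-test is the natural reading.

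**2. Reproduce the enrolled size.**
- Increase by 20%: 42 × 1.2 = 50.4 (25.2 per arm). Rounded down, this is the stated 50 (25 per arm).
- Divide by the retained proportion: 42/(1 − 0.20) = 52.5, so 53 in total. Per arm, 21/0.8 = 26.25, so 27 per arm and 54 in total.

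The stated 50 agrees with the first calculation only, and only after rounding down.

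**3. What remains after the anticipated loss.**

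| Enrolled | Per arm | Per arm after 20% loss | Covers 21 per arm? |
|---|---|---|---|
| 50 | 25 | 25 × 0.8 = 20.0 | No |
| 52 | 26 | 26 × 0.8 = 20.8 | No |
| 54 | 27 | 27 × 0.8 = 21.6 | Yes |

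**4. The dropout that 50 does allow.** 1 − 42/50 = 8/50 = 16%, or 4 of 25 women in each arm. A 20% loss is 5 of 25.

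**5. Power, by the method that reproduced 42** (*d* = 0.9, two-sided alpha 0.05).

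| Evaluable per arm | Power |
|---|---|
| 20 | 79.2% |
| 21 | 81.2% |

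With 20 per arm, the smallest difference detectable with 80% power is *d* = 0.91.

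**6. Sensitivity at 20 per arm.** The normal approximation gives 81.2% and a one-sided t-test 87.5%, but neither reproduces the stated 42. If 0.9 is a rounded 0.89, which still requires 21 per arm, power by the two-sided t-test is 78.3%. Power under the planned repeated measures ANOVA cannot be calculated: the plan gives no pre-post correlation and does not say whether 0.9 refers to change or to post-intervention values.

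**The case against.** The strongest reply is that very little follows from the error. The shortfall is two women, power is 0.8 percentage points below 80%, and the detectable effect moves from 0.90 to 0.91. That is well within the uncertainty of an effect size given to one decimal and taken from a single previous study. The title calls the study a pilot, and the plan gives no basis for expecting 20% dropout rather than 16%. The power figure also rests on a test the plan does not name and which differs from the planned ANOVA. Finally, the document is written in the past tense, so enrolment may be over and a larger target of no use.

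Most of this stands as a statement about weight. The loss of power is minor, and the power figure must be given with its assumed test. It does not remove the inconsistency. The plan chose to state a formal minimum, a power and a dropout rate, and 40 is below 42 whatever test was used and however the study is labelled. Reading the 20% as a share of the 42 does not rescue the figure either: 50.4 rounds up to 51, or 52 with equal arms.

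**Conclusion.** The concern holds. Fifty women with 20% dropout leaves 40 evaluable (20 per arm), two below the stated minimum. The enrolment that matches the plan's own inputs is 53, or 54 with equal arms, so the stated figure is 3 to 4 women too low. This part uses only the plan's figures and needs no assumption about the test.

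The effect on power is small: 79.2% against the stated 80%, assuming a two-sided two-sample t-test at a standardised difference of 0.9. That the adjustment was made by multiplying by 1.2 is inferred from the fit, since no formula is given. The error is certain and its consequence modest. It should be corrected, but it does not by itself undermine the design.

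**What to change.** Restate what 50 women provide, without enrolling more. Suggested wording:

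> Fifty women (25 per group) allow for 16% dropout while retaining 42 evaluable. At 20% dropout, 40 evaluable women give 79% power for a standardised difference of 0.9 (two-sample t-test, two-sided alpha 0.05).

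The sponsor should confirm the test in brackets against the G*Power settings used, and change the power figure if they differ.

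If the 20% allowance and 80% power are both to be kept as stated, and enrolment is still open, the inflated size is 54 (27 per group), four more women than planned.

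The cost of the first option is one sentence and a slightly less favourable dropout allowance or power.

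### The planned pre/post ANOVA does not adjust for baseline pad-test leakage, so part of any chance baseline difference enters the treatment comparison; ANCOVA on baseline would remove it at no cost

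*Combined protocol and SAP*

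**What the plan says.** Under Procedure (Interventions), allocation is covered by one statement: "Subjects were randomized into two treatment groups". The sequence method, blocking, minimisation and stratification are not described. The Sample size calculation section gives "statistical power of 80%, and a 1:1 allocation ratio" and plans 50 women, 25 per group, after an allowance for dropout.

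The same section names the 1-hour pad test as primary outcome. Measurements places it at baseline and after six weeks. Participants requires symptoms confirmed by questionnaire and sets no lower or upper limit on leakage in grams, so light and heavy leakers can enter together.

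Statistical analysis gives the method in one sentence: "A two-way repeated measures ANOVA was employed with the outcome metrics, both pre- and post-intervention". It does not say whether group, time or group-by-time is the treatment test, and it mentions no covariate. The documents give no SD and no pre-post correlation for the pad test.

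**The concern.** In a pre/post ANOVA with two time points, the group-by-time term is a comparison of changes from baseline. Change depends on where a woman starts: those who leak heavily on the baseline test tend to fall further through regression to the mean alone. If one arm happens to start heavier, it will on average show a larger fall without any HIFEM effect, and the lighter arm a smaller one.

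Nothing in the plan as written deals with this. No balancing on baseline leakage is described, and the model has no baseline term. In a trial of 50 women, the single estimate reported could be moved toward or away from HIFEM, and a baseline table showing unequal leakage would leave the result open to dispute. The analysis also gives up precision that the baseline measurement could supply.

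**Working it through.** **Inputs.** From the documents: 25 per group, alpha 0.05, power 80%, effect size 0.9, measurements at baseline and week 6. Assumed, because the documents are silent: two-sided testing, simple 1:1 randomisation, equal pre and post variances, group-by-time as the treatment test, and rho of 0.3 to 0.7. SD means the SD of the pad-test value.

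**1. The plan's own figure.** The protocol says "The a priori power analysis utilized an estimated effect size of 0.9" and that "a minimum sample size of 42 (21 per arm) was established". A two-sample t-test with d = 0.9 and two-sided alpha 0.05 gives 21 per arm (power 81.2%), so 42 reproduces. One-sided testing would give 16 per arm, which supports the two-sided reading. The match is to a plain two-group comparison with no baseline term.

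**2. Size of chance imbalance.** The standard error of the difference in baseline means is sqrt(2/25) = 0.283 SD.

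- P(difference above 0.3 SD) = P(|Z| > 0.3/0.283) = 29%
- P(difference above 0.5 SD) = P(|Z| > 0.5/0.283) = 7.7%, about 1 in 13
- With 20 per arm (50 x 0.8 = 40 women left after 20% dropout): standard error sqrt(2/20) = 0.316 SD, and P(above 0.5 SD) = 11%

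Skewed values change this little: with lognormal leakage (assumed log-SD 0.8 to 1.2), P(above 0.5 SD) at 25 per arm is 7.6% to 6.8%.

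**3. Carry-over.** Given a baseline imbalance D, the expected shift in the change-score difference is -(1 - rho) x D. The ANCOVA estimate shifts by zero.

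**4. False-positive rate given the imbalance.** The critical value is 1.96 x sqrt(2(1 - rho)) x 0.283, and the conditional standard error is sqrt(1 - rho²) x 0.283. Example at rho = 0.5, D = 0.5: critical value 0.554, shift 0.25, conditional standard error 0.245. Then (0.554 - 0.25)/0.245 = 1.24, and the two tails together give 10.8%.

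**5. Precision.** With unit variances, the change score has variance 2(1 - rho) and the ANCOVA residual 1 - rho². The ratio is (1 + rho)/2.

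| Assumed rho | Shift at D = 0.5 SD | False positives at D = 0.5 SD | ANCOVA / change-score error variance | Simulated power at a true effect of 0.9 SD, change score vs ANCOVA |
|---|---|---|---|---|
| 0.3 | 0.35 SD | 12.9% | 0.65 | 75.2% vs 90.0% |
| 0.5 | 0.25 SD | 10.8% | 0.75 | 87.8% vs 94.6% |
| 0.7 | 0.15 SD | 8.5% | 0.85 | 97.9% vs 99.1% |

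**6. Simulation check** (20,000 trials per scenario, 25 per arm). Over all randomisations the change-score test has mean bias of about zero and a type I error of 4.8% to 5.0% at these values of rho. Among trials with an imbalance above 0.5 SD, its type I error is 19.5%, 15.7% and 10.3% at rho 0.3, 0.5 and 0.7. ANCOVA stays near 5% in the same trials.

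**7. If the group main effect were the treatment test instead.** The shift is (1 + rho)/2 x D: at D = 0.5, 0.33 to 0.43 SD for rho 0.3 to 0.7, in the same direction as the imbalance.

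**The case against.** The strongest reply is that randomisation already protects the comparison. The test is unbiased and holds 5% over all allocations. A 0.5 SD imbalance is a 1-in-13 event, and the title calls the study a pilot. All of that stands. It limits the point to conditional bias and lost precision; it does not make an unadjusted analysis the better choice.

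A second reply concerns rho. If baseline leakage predicts week-6 leakage strongly, carry-over is small: at rho = 0.9 a 0.5 SD imbalance shifts the estimate by only (1 - 0.9) x 0.5 = 0.05 SD. The 0.35 SD figure needs a weak correlation of 0.3. This is correct, and the documents do not say where rho lies, so the size has to be given as a range.

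Third, the protocol is silent on stratification and does not rule it out. A reader might infer that allocation was deliberately unstratified; the text does not support that. The missing baseline term in the analysis sentence is the firmer ground.

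A reader might also infer that the cure is to stratify by baseline leakage. Stratifying at the median helps an unadjusted change-score analysis somewhat: in simulation it cut the variance of the difference by about 6% to 21% on a normal scale, but only about 5% on an assumed lognormal gram scale. Once baseline is a covariate it adds at most about 2%. It also needs a cut-off in grams fixed in advance, for which the documents give no basis.

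**Conclusion.** The point holds as an analysis recommendation. As written, the model leaves baseline pad-test leakage unadjusted, and a fraction (1 - rho) of any chance difference enters the group-by-time comparison. At a 0.5 SD imbalance that is 0.35 to 0.15 SD, or 39% to 17% of the planning effect of 0.9 if both are in the same SD units.

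Two stronger readings should be set aside. One is that a sizeable imbalance is likely: 0.3 SD is exceeded in about 3 trials in 10 and 0.5 SD in about 1 in 13, so it is not rare, but it is not the expected outcome. The other is that the planned test is invalid or that the whole imbalance passes into the result. It keeps its error rate overall, and only part of the imbalance carries over.

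The size rests on the assumed rho, equal pre and post variances, and group-by-time being the treatment test. More generally the carry-over is one minus the slope of the week-6 value on baseline. If leakage becomes less variable after treatment, that slope falls and the carry-over grows.

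**What to change.** In Statistical analysis, replace the single sentence on the model with a statement that the primary treatment test is an ANCOVA of week-6 1-hour pad-test leakage on group, with the baseline pad-test value as a continuous covariate, two-sided at 0.05. Report the adjusted difference with its 95% confidence interval. Use a log scale if the weights are skewed, and fix the rule for choosing the scale and for handling zero weights in advance. The same model can serve the questionnaire score and bladder neck movement. If the repeated measures ANOVA is kept as a supporting analysis, name its treatment term.

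The cost is a few lines of text: no extra women, visits or measurements. If outcome data have already been examined by group, label the change as post hoc here and pre-specify it for the trial that this pilot prepares.

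Under Procedure, state how the sequence was generated and whether allocation was blocked or stratified. Stratified blocks on baseline leakage are optional. If used, they require the baseline pad test before allocation and one list per stratum, and the stratum should be in the model alongside the continuous baseline value.

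### The planned repeated-measures ANOVA leaves the baseline pad test unused as a covariate; a baseline-adjusted ANCOVA would usually estimate the same treatment effect more precisely

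*Combined protocol and SAP*

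**What the plan says.** The Objectives section sets out to assess HIFEM "combined with Pelvic-Floor-Muscle-Training (PFMT) versus PFMT alone on urine leakage and quality of life". Under Procedure, "Subjects were randomized into two treatment groups". Under Measurements there are two assessments: "Evaluations conducted at baseline and after the six-week intervention". The Statistical analysis section names the software ("All data were analyzed using IBM SPSS Statistics for Windows, Version 26.0") and then the method: "A two-way repeated measures ANOVA was employed with the outcome metrics, both pre- and post-intervention".

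That is the whole analysis plan. It does not say whether group, time or group-by-time answers the objective, it defines no effect estimate or confidence interval, and no other section adds a baseline covariate.

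The Sample size calculation section rests on "observations of the primary outcome (the 1hour pad test) in a previous study" and states: "The a priori power analysis utilized an estimated effect size of 0.9". It does not say which SD standardises the 0.9, and it gives no pre-post correlation.

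**The concern.** A two-way repeated-measures ANOVA produces three tests. The time effect does not compare the arms. The group main effect compares pre/post averages, and since treatment cannot affect the baseline value, it estimates only half the treatment effect. Only group-by-time tests the objective, and in this design it equals a t-test on change scores.

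The change score implicitly fixes the slope of the 6-week value on baseline at 1. ANCOVA estimates that slope instead. Under randomisation both target the same between-group difference, but unless the true slope is close to 1 the change score carries baseline noise that ANCOVA removes. What is at stake is precision: a wider interval for the effect of HIFEM than the collected data allow. The unnamed term is the smaller problem, but it leaves open which of the three tests counts.

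**Working it through.** **Inputs from the protocol.** 21 per arm before the dropout allowance, effect size 0.9, alpha 0.05, power 80%, 1:1 allocation, two arms, two time points. **Assumed, because not given:** pre-post correlation ρ (0.3, 0.5, 0.7) and s = post SD / pre SD (0.75, 1, 1.25), the same in both arms; alpha two-sided.

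**1. The plan's own figure.** A two-sided two-sample t-test (noncentral t) with d = 0.9 has power 79.2% at 20 per arm and 81.2% at 21. The stated 21 per arm (42 in total) reproduces.

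**2. Variances**, in units of the squared pre SD, with n = 21:
- Group-by-time (change score): (2/n)(1 + s² − 2ρs), 40 df.
- ANCOVA: (2/n)·s²(1 − ρ²)·[1 + 1/(2n − 4)], 39 df. The bracket is the average cost of estimating the slope: 1 + 1/38 = 1.0263.

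Since 1 + s² − 2ρs = s²(1 − ρ²) + (1 − ρs)², the variance ratio, change over ANCOVA, is

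[1 + (1 − ρs)² / (s²(1 − ρ²))] / 1.0263.

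Example, s = 1 and ρ = 0.5: (1 + 0.25/0.75)/1.0263 = 1.30. The interval-width ratio is the square root times t(40)/t(39) = 2.0211/2.0227, which gives 1.139.

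| s | Variance ratio at ρ = 0.3 / 0.5 / 0.7 | Interval-width ratio |
|---|---|---|
| 1 | 1.50 / 1.30 / 1.15 | 1.223 / 1.139 / 1.070 |
| 0.75 | 2.12 / 1.88 / 1.74 | 1.454 / 1.369 / 1.318 |
| 1.25 | 1.24 / 1.09 / 0.99 | 1.114 / 1.044 / 0.996 |

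**3. Where ANCOVA loses.** The ratio is lowest when the slope ρs equals 1: 1/1.0263 = 0.974, a width ratio of 0.986. This occurs, for example, at s = 1.25 and ρ = 0.8. The ratio falls below 1 only for ρ above about 0.95 (s = 1) or between about 0.68 and 0.88 (s = 1.25), and never at s = 0.75.

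**4. Power at 21 per arm**, equal SDs, 0.9 taken on the week-6 SD. Standard errors are √[(2/n)·2(1 − ρ)] for group-by-time and √[(2/n)(1 − ρ²)·1.0263] for ANCOVA. The group main effect estimates (0 + 0.9)/2 = 0.45 with standard error √[(2/n)(1 + ρ)/2].

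| ρ | Group-by-time | ANCOVA | Group main effect | Per-arm n for 80% power, group-by-time vs ANCOVA |
|---|---|---|---|---|
| 0.3 | 67% | 84% | 42% | 29 vs 20 |
| 0.5 | 81% | 90% | 38% | 21 vs 17 |
| 0.7 | 96% | 98% | 34% | 13 vs 12 |

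If 0.9 is instead on the change-score SD, group-by-time has 81% throughout and ANCOVA has 94%, 90% and 86%.

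**5. Simulation** (60,000 normal trials per setting). Variance ratios were 1.50 / 1.30 / 1.14 (s = 1), 2.12 / 1.88 / 1.74 (s = 0.75) and 1.25 / 1.09 / 1.00 (s = 1.25). Power with equal SDs was 67.4 vs 83.8%, 81.4 vs 90.0% and 95.6 vs 97.5%. The group main effect averaged 0.45 against a true 0.9. Type I error was 4.8–5.2% for both tests.

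**The case against.** **The planned test is not wrong.** Group-by-time is unbiased, and 21 per arm is consistent with it if the 0.9 is on change scores, or on the week-6 scale at ρ = 0.5. The title also calls the trial a pilot. This stands, and it is why the point is a recommended improvement and not an error. Pilot status does not remove it: the trial is sized for 80% power on a primary outcome.

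**The gain rests on assumptions.** Neither ρ nor s is in the documents, and over the grid the variance ratio runs from 2.12 down to 0.99. This also stands. The direction can be relied on for most of that grid; no single magnitude can. The asymmetry still favours ANCOVA, because its largest average loss is small.

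**The 2.6% cost is an average.** It is the largest repeated-sampling loss over all slopes, averaged over chance baseline imbalance. In a single trial the inflation is 1 + (n/2)d²/Sxx, where d is the baseline mean difference and Sxx the pooled within-group sum of squares. Its 95th percentile is about 1.10 and its 99th about 1.18. An unlucky trial can therefore pay more. The averages in the comparison already include such trials.

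**The deciding term is obvious.** Group-by-time is indeed the natural reading, and nothing in the documents suggests that the main effect was intended. The precision argument holds on that reading.

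**The analysis may be finished.** The text is in the past tense, and the documents do not settle the timing. If it is finished, replacing the primary analysis after seeing the data would not be defensible, and only a labelled additional analysis remains.

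**Pad weights may be skewed.** The plan does not address this. Change scores face the same difficulty, and ANCOVA remained more precise in lognormal checks.

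**Conclusion.** The concern holds as a matter of efficiency and pre-specification. With equal SDs and ρ from 0.3 to 0.7, the planned comparison has 1.15 to 1.50 times the variance of a baseline-adjusted one. The advantage is larger if the post SD shrinks to 0.75 of the pre SD; at 1.25 times it is smaller and can reverse slightly. These figures assume 21 completers per arm, approximately normal data, and the same ρ and s in both arms. They do not show bias, inadequate power or a wrong sample size. The missing deciding term is a secondary but real gap. The trial should make the change, although the planned analysis is usable without it if group-by-time is the test reported.

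**What to change.** If the analysis has not been run, replace the ANOVA sentence with:

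> The primary analysis is an ANCOVA of the 6-week 1-hour pad test on treatment group with the baseline pad test as covariate. The treatment effect is the adjusted between-group difference with its 95% CI. ICIQ-UI-SF and bladder neck movement are analysed in the same way.

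If the data have already been analysed, keep the planned test, report the ANCOVA beside it, and label it as added later. If the ANOVA is retained in either case, state that group-by-time is the deciding term.

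The cost is one sentence, with the same data and software and no more participants. Statistically it is at most about 2.6% of variance, averaged over baseline imbalance, and one residual degree of freedom (39 against 40 at 21 per arm).

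### The primary pad weight goes untransformed into a repeated measures ANOVA; if leakage is skewed and treatment acts proportionally, power can fall well below the stated 80%

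*Combined protocol and SAP*

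**What the plan says.** The sample size section makes the 1-hour pad test the primary outcome. Under Measurements: "The total amount of urine leakage was measured by weighing the pad after performing several standardized activities over the course of an hour". The Statistical analysis section then says only this about method: "A two-way repeated measures ANOVA was employed with the outcome metrics, both pre- and post-intervention". It names no transformation, distribution check, rank or robust alternative, or sensitivity analysis, and does not say which ANOVA effect is the primary test. Analysis on the gram scale is inferred from the absence of a transformation; the documents do not state it.

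On size: "The a priori power analysis utilized an estimated effect size of 0.9", with "statistical power of 80%, and a 1:1 allocation ratio", and "a minimum sample size of 42 (21 per arm) was established". The effect comes from an earlier study's pad-test results, but no mean, SD or pre-post correlation is given. Nor is it said whether 0.9 refers to post-treatment values, to change, or to another scale. Entry rests on questionnaire-confirmed symptoms, with no lower or upper limit on pad weight.

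**The concern.** A pad weight has a floor at zero and no ceiling, and no woman can lose more than she leaks at baseline. A woman leaking 2 g can improve by at most 2 g; one leaking 50 g can improve by 50 g. With no entry range, the variance of the change is likely to grow with baseline, and a few heavy leakers can then carry much of the comparison. With about 20 women per arm, the result for the only powered outcome could depend on one or two of them, and the test could have much less than the planned power. A mean difference in grams would then also be a weak basis for planning the main trial that this pilot is meant to inform.

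**Working it through.** **1. The plan's own figure.** A two-sample t-test at d = 0.9 with two-sided alpha 0.05 needs 21 per arm (exact power 81.2%), which reproduces 42. With 25 enrolled per arm and 20% dropout, 25 × 0.8 = 20 remain per arm, and power is 79.2%.

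**2. The test that the plan implies.** With two time points, the group-by-time effect of the ANOVA equals a t-test on change. For normal data with d = 0.9 on post-treatment values, the effect on change is 0.9/√(2(1−ρ)):
- ρ = 0.3: 0.9/1.183 = 0.76, power 67%
- ρ = 0.5: 0.9/1.000 = 0.90, power 81%
- ρ = 0.7: 0.9/0.775 = 1.16, power 96%

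So the stated power already depends on an unstated correlation before any skew enters.

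**3. Skewed data, effect fixed at 0.9 in raw units.** Assumptions, none of them from the documents: log-normal weights, log-scale correlation 0.5, mean baseline 10 g, values below 0.5 g recorded as 0, proportional effect, 21 per arm. The treatment ratio r solves (1−r)/(CV·√((1+r²)/2)) = 0.9.
- CV 0.75: r = 0.472, since 0.528/(0.75 × 0.782) = 0.90
- CV 0.5: r = 0.625, since 0.375/(0.5 × 0.834) = 0.90

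Simulated power (%), 10,000 trials per cell:

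| CV; change under PFMT alone | Group-by-time, grams | Group-by-time, log(g+1) | ANCOVA, grams | ANCOVA, log(g+1) |
|---|---|---|---|---|
| 0.75; 30% cut | 45 | 91 | 94 | 98 |
| 0.75; none | 67 | 93 | 94 | 98 |
| 0.5; 30% cut | 47 | 85 | 92 | 95 |

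Moving from the first to the third column of figures adds baseline as covariate and leaves the scale alone. It recovers 27 to 49 points (94−67, 94−45). Moving from the third to the fourth changes only the scale, and adds 3 to 4 points.

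**4. Scale alone, as skew grows.** Baseline as covariate on both scales, 50% proportional reduction, 20 per arm, other assumptions as above:

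| CV | ANCOVA, grams | ANCOVA, log(g+1) | Gain (points) |
|---|---|---|---|
| 0.75 | 89 | 95 | 6 |
| 1.0 | 67 | 83 | 16 |
| 1.5 | 38 | 60 | 22 |

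In the same setting with no change under PFMT alone, group-by-time power (grams versus log) is about 61 versus 88, 40 versus 70 and 21 versus 47. At CV 1.0, one woman of 40 supplies a median of about 31% of the sum of squares of change.

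**5. If the 0.9 is on the log scale.** With 21 per arm, log-SD 0.5 to 1.5, correlation 0.3 to 0.7 and PFMT alone leaving 0.7 of baseline, group-by-time power is 12-55% in grams and 67-96% in logs. ANCOVA gives 43-95% and 84-98%.

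**6. Type I error.** For the group-by-time test in grams it was 3.0-4.5% in the null cells run: slightly conservative, not inflated.

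**The case against.** The strongest reply is that the cause is the missing baseline adjustment and not the gram scale. That largely stands for the table in step 3, where ANCOVA in grams reaches 92-94%. Skew is not even needed for a shortfall: with normal data, CV 0.5, a proportional effect and a 30% cut under PFMT alone, group-by-time power is 47%. The reply does not cover step 4, where adjustment is already in place and grams still lose 16 to 22 points at CV 1.0 and above.

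A second reply is that 0.9 may be an additive shift in raw change-score SD units; the gram analysis then keeps 82-91% power even with log-normal data. The documents do not exclude this. But under log-normal weights such a shift would put 71-84% of treated women below zero grams at log-SD 1.0 and 5-25% at log-SD 0.5, so it is a realistic alternative only where skew is mild.

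A third reply concerns the remedy. Back-transforming log(grams+1) gives a ratio of (grams+1). With a true leakage ratio of 0.50 and CV 0.75, it reads about 0.66 at a mean baseline of 2 g, 0.60 at 5 g, 0.56 at 10 g and 0.53 at 20 g. That stands, and it governs how the result must be labelled.

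A reader might also infer that heavy leakers will dominate this trial, that its power is about 45%, or that a positive result would be unsafe. The documents support none of these. They give no unit, mean, SD, skewness or correlation for the pad test, and type I error is held.

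**Conclusion.** The concern holds in conditional form. The plan applies a normal-theory ANOVA to a zero-bounded weight with an open upper end and provides no transformation or rank method. If leakage is right-skewed and treatment acts proportionally, a few women can dominate and the planned group-by-time test can have about 45-67% power against the stated 80% (21 per arm, raw d = 0.9, CV 0.5-0.75). Most of that loss is due to unadjusted change. The part due to scale alone is 3-4 points in those cells; for a 50% reduction with 20 per arm it is about 6, 16 and 22 points at CV 0.75, 1.0 and 1.5. The distribution, the correlation, the baseline level and the scale of the 0.9 are all assumed. The matter is one of power and of how the effect is summarised, not of false positives. It merits a change because that change is small.

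**What to change.** Prespecify the primary pad-test comparison as post-treatment log(grams+1) between arms, with baseline log(grams+1) as covariate. Name a rank-based ANCOVA as the sensitivity analysis in case many pads are dry. Label the back-transformed effect, with its 95% CI, as a ratio of (grams+1), not a ratio of leakage. Beside it, report raw-gram means and medians by arm, and the mean difference with a bootstrap 95% CI. State also which scale the 0.9 refers to.

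The cost is a few sentences in the Statistical analysis section and a computed variable for each time point in SPSS. There are two downsides. The effect scale is less direct and depends on the added constant. If the data are in fact additive and normal, about 4 points of power are lost: 84% on the log scale against 88% in grams with baseline as covariate, in the one simulation run for that case.
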